AZVUDINE 2mg, 3mg and 4mg groups showed good safety. The total incidence of drug-related adverse events (85.7%, 92.9%, 93.0%, respectively) and the degrees of intensity were similar to those in the 3TC group (88.4%). The difference was not statistically significant (P >0.05). Among all adverse reactions, only 3 adverse reactions caused withdrawal in the AZVUDINE 3mg (2.4%), AZVUDINE 4mg (2.3%) and 3TC (4.7%) groups, dizziness, followed by increased ALT, GGT, AST and blood uric acid. The adverse reaction of dizziness was slightly higher in grades 1 and 2. Grade 3 adverse reaction occurred only in the AZVUDINE 3mg group and the 3TC group. The incidence was 2.4% and 4.7%, respectively, and no grade 4 adverse reaction of dizziness occurred. However, the adverse reactions of dizziness that occurred during the study may be related to the EFV (Efavirenz) drug.

In summary, AZVUDINE combination treatment with TDF and EFV significantly inhibited HIV-1 RNA replication, and the treatment effect is currently comparable to the first-line treatment plan 3TC + TDF + EFV. The treatment showed good safety, so that the three AZVUDINE dose groups and the 3TC group were similar in the total incidence and severity of adverse reactions.

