A potential direct benefit to participants who receive this drug during the study can be expected to be the conversion of the viral nucleic acid to negative in a shorter time. It is important to note some risks and benefits attached to the randomized trial model, such as the possibility of the research participant being allocated to the PLACEBO group, i.e., without intervention of the experimental drug, which may be a promising treatment, but is not yet available in clinical practice. However, participants in the PLACEBO group will have the assistance recommended for treatment of COVID-19, and all participants will have constant monitoring of the progress of the disease through consultations and examinations. In addition, participation in a clinical trial requires greater availability of the study participant, as there is a need for frequent follow-up.

There will be an intensive follow-up of the patient in the hospital unit. The evaluations will be made by trained professionals and any alterations will be identified and appropriate actions will be taken to minimize and/or recover them. In addition, the participant will have access to and guidance regarding all the tests performed. At any time, the participant may have access to all information obtained about him or her from this study, or about the overall results of the study after its termination. Withdrawal and/or termination of the trial will not affect the medical care offered to the participant, as control visits are scheduled.

All medical information will be confidential and only the study team will have access to avoid a breach of confidentiality. At no time will the participant's name or any information about their health be provided to anyone other than the study team. The information will be confidential and used only for the purpose of this research. All reasonable measures to avoid breaching the participant's identity and confidentiality will be taken. These include access to study documents only for those on the research team,

storage of printed documents in a locked file in a location with restricted access, and storage of electronic data in a database with secure access via individual username and password only for the researchers and other members of the research team.

By proving the clinical efficacy and safety of AZVUDINE, society will be able to benefit from an effective treatment against the new coronavirus.

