4. OBJECTIVES AND OUTCOMES OF THE STUDY

Primary Objectives	Primary Outcome	
To evaluate the efficacy and safety of AZVUDINE (FNC) versus placebo in patients infected with moderate to severe stage SARS-COV-2;	 Proportion of participants with clinical status improvement [Period: until D15, approximately 14 days]. The criterion for a participant to have an improvement in clinical status is a decrease on the WHO Clinical Improvement Ordinal Scale in at least one category compared to screening (WHO, Jun/2020). 	

Secondary Objective	Secondary Outcome	
To evaluate the clinical	Proportion of participants with a clinical outcome of cure	
outcome between the	during the study; [Period: until D15, D21, and D28,	
AZVUDINE (FNC) group	approximately 14-30 days].	
versus placebo in	 The clinical endpoint of cure is defined in this 	
patients infected with	protocol as the absence of viral RNA in	
moderate to severe stage	collected samples and clinical conditions for	
SARS-COV-2;	hospital discharge ⁴ .	
,	• Time to normalization of body temperature (below 37.6°C	
	axillary); [Period: until D15, D21 and D28, approximately	
	14-30 days]	
	• Time to improvement of diarrhea, myalgia, fatigue,	
	malaise, cough, dyspnea, and headache; [Period: until	
	D15, D21, and D28, approximately 14-30 days].	
	• Changes in liver and kidney function baselines, and	
	inflammatory and immunological markers: [Period: until	
	D15, D21 and D28, approximately 14-30 days]	
	 Lab tests performed on days D1, D3, D5, D7, 	
	D9, D13, D15, D21, D28, and D60.	
	• Evaluation of the time to negative conversion of the	
	SARS- CoV-2 viral load by RT-PCR between AZVUDINE	
	(FNC) group and control group; [Period: until D15, D21	
	and D28,approximately 14-30 days].	
	Evaluation of the number of cycles for the detection of	
	SARS-CoV-2 viral load by RT-PCR and application of the	

⁴ According to the WHO Working Group on Characterization and Clinical Management of COVID-19 Infection (July, 2020), clinical and virological absence of infection (non-detectable RT-PCR) is suggestive of CURE for initially infected participants.

standard curve for viral load calculation; [Period: until D15, D21 and D28, approximately 14-30 days].

- Analysis of the relationship between the calculated viral load and the clinical progress of participants in the AZVUDINE (FNC) group compared to the control group; [Period: until D15, D21 and D28, approximately 14-30 days].

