for the last 3 patients who entered the group last, all other patients were cured and discharged. In terms of safety events, with the exception of individual patients who had skin rash or elevated ALT, other adverse events were probably unrelated and no serious adverse events were reported. The adverse reactions in this study were mainly ALT and AST increase, mainly grade 1 adverse reaction, only 1 case of ALT elevation was grade 3 adverse reaction, and the outcome was normalization, and the adverse reactions were common adverse reactions of antiviral drugs. No unexpected adverse reactions occurred. There were no serious adverse events, serious adverse reactions, major adverse events, or death events in the study period.

Recently (2020), the journal NATURE published the article *AZVUDINE (FNC): a* promising clinical candidate for *COVID-19 treatment*⁸, which considers AZVUDINE a promising candidate for the treatment of COVID19, demonstrating its potential in inhibiting viral replication.

[figure not shown]

Figure 4: Mechanism of action of AZVUDINE a) Azvudine nucleoside-based anti-HIV clinical candidate (FNC) for the treatment of COVID-19. Structure of SARS-COV-2 RNA showing a cytosine subunit; b) Diagram showing the RNA replication process of SARS-

COV-2 blocked by FNC; c) Proposed mechanisms of FNC to inhibit SARS-COV-2 activity¹.

To minimize study bias, research participants will be randomized and treatment will be administered blindly, both by research center staff and to participants. The research center's standard treatment will be used to avoid any complications/aggravations of the disease and PLACEBO will be used for masking purposes only.

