11.3. METHOD OF STATISTICAL ANALYSIS

All statistical tests will be two-sided tests.

- If the p-value is ≤0.05, it is considered that there is statistical significance in the test (unless otherwise specified).
- The quantitative indices describe the mean value, standard deviation, median, minimum value, maximum value, lower quartile (Q1), upper quartile (Q3) to be calculated, and the rank indices describe the frequency and percentage of cases.
- Comparison of the two groups under general conditions will be analyzed with appropriate methods according to the types of indicators. Student's ttest or Mann-Whitney test will be used to compare the groups for quantitative data. Chi-square test or Fisher's exact test will be used for categorical data.
- The selected cases should be grouped and at the end of the study determine the three analysis data sets (FAS, PPS, SS).
- For the analysis of demographic information and baseline eigenvalues, the mean value, standard deviation, quartiles, minimum value and maximum value should be calculated for numeric variables. For categorical data, frequency and percentage will be calculated.
- For analysis of medication and drug combination adherence one should calculate the percentage of individuals whose medication adherence is at

least 80-100%. An analysis of the classification of the combination of drugs should also be done.

• For analysis of the primary effectiveness indicator:

Primary Goal

To evaluate the **efficacy and safety of** AZVUDINE (FNC) versus placebo in patients infected with moderate to severe stage SARS-COV-2;

Analysis method:

For the efficacy analysis a logistic regression model will be used with the dependent variable "The proportion of participants with clinical improvement [Period: until D15, approximately 14 days]" and independent variables allocation group, AZVUDINE (FNC) or PLACEBO. For the Safety analysis a logistic regression model will be used with the dependent variable "occurrence of serious adverse events" and independent variables allocation group, AZVUDINE (FNC) or PLACEBO. As a support analysis, with exploratory character, both for efficacy and safety, covariate models will be built as well as other variables that present, in the univariate analysis, statistical significance.

Secondary objective

To evaluate the **clinical outcome** between the AZVUDINE (FNC) group versus placebo in patients infected with moderate to severe stage SARS-COV-2;

Analysis method:

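### The safety half of the primary objective is analysed by a test of difference on serious adverse events, in a trial sized on efficacy alone; if the control rate is below about 11%, a non-significant result says little about safety

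*Protocol*

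**What the plan says.** Protocol section 4 gives the primary objective as "To evaluate the efficacy and safety of AZVUDINE (FNC) versus placebo" in moderate to severe patients. The only primary outcome listed beside it is clinical improvement up to D15.

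Section 11.3 names the analysis for each half of that objective. For safety it says "For the Safety analysis a logistic regression model will be used with the dependent variable" "occurrence of serious adverse events", with allocation group as the independent variable. Models with covariates are exploratory support. The general rules at the head of the section are "All statistical tests will be two-sided tests" and "If the p-value is ≤0.05, it is considered that there is statistical significance in the test", the latter unless otherwise specified.

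The table later in section 11.3 adds t, Mann-Whitney or chi-square comparisons for the frequency and intensity of SAEs, and listings follow it. Section 11.3 also allows chi-square or Fisher's exact test for categorical data in general.

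Section 11.1 derives 81 evaluable and 90 randomised per arm from expected improvement proportions of 66.7% and 28.1%. Its only margin, 0.205, belongs to that efficacy calculation. The protocol gives no expected SAE rate, no precision for the safety comparison and no excess of SAEs to be ruled out.

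Section 2.6.3 ends its discussion of benefit with "By proving the clinical efficacy and safety of AZVUDINE, society will be able to benefit" from an effective treatment.

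**The concern.** A test of difference can show harm, but failing to show harm is informative only if the trial had a good chance of showing it. Here the protocol fixes the model for a primary objective, and the number of participants was chosen without regard to that model. If SAEs are uncommon, the likely result is a non-significant odds ratio that is compatible both with no effect and with a large excess. A report that follows section 11.3 literally would have little else to say on the safety half of its primary objective.

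The protocol's own background points to possibly low counts. Section 5.1.2 says of HOPE-4 that "other adverse events were probably unrelated and no serious adverse events were reported", and section 8.1 keeps hospitalisation for disease progression out of SAE reporting. With very few events an arm may have none, and the ordinary maximum-likelihood odds ratio then does not exist as a finite number.

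**Working it through.** **Inputs.** From the protocol: 90 per arm, or 81 after 10% dropout (11.1); any SAE, yes or no, regressed on allocation, two-sided, p ≤0.05 (11.3). Not in the protocol: the control SAE rate, assumed here to be 2%, 5%, 10%, 15% or 20%.

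**1. The protocol's own size.** n = (z₁₋α + z₁₋β)² × [p1(1−p1) + p2(1−p2)] / (delta − margin)². With 0.667, 0.281, 0.386, 0.205, a one-sided α of 0.05 and 80% power this gives 80.04, so 81; 81/0.9 = 90. The figure reproduces, and every input concerns clinical improvement. (It reproduces only with a one-sided α, which is a separate matter.)

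**2. Chance of missing a doubling.** For each assumed rate p, all pairs of binomial counts (control p, azvudine 2p) were enumerated and the probability of p ≤0.05 in the direction of harm was summed. Wald tests with an empty arm were counted as non-significant.

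| Control to azvudine | Missed, 90 per arm (likelihood ratio / Wald) | Per arm for 80% power |
|---|---|---|
| 2% to 4% | 83% / 99% | 1141 |
| 5% to 10% | 74% / 81% | 435 |
| 10% to 20% | 52% / 55% | 199 |
| 15% to 30% | 31% / 32% | 121 |
| 20% to 40% | 16% / 16% | 82 |

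The simple pooled z formula agrees: power at 90 per arm is 24.5%, 46.7%, 67.6% and 83.9% for control rates of 5%, 10%, 15% and 20%. Power passes 50% at a control rate of 10.5% (likelihood ratio) or 11% (Wald), and 80% at about 19%. At 81 per arm the 10% to 20% doubling is missed 56% / 58% of the time.

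**3. What a non-significant result leaves open.** Suppose 18/90 v 9/90. Log odds ratio = ln(18/72) − ln(9/81) = 0.811; SE = √(1/18 + 1/72 + 1/9 + 1/81) = 0.439; z = 1.85; p = 0.065. The odds ratio is 2.25 (95% CI 0.95 to 5.32). The Newcombe interval for the excess is 10.0 points (−0.5 to +20.5).

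If the arms are equal, the Newcombe upper limit is √[(u − p)² + (p − l)²], where l and u are the Wilson limits of one arm. At 9/90, l = 5.4% and u = 17.9%, so the limit is √(7.9² + 4.6²) ≈ 9.2 points. At 5% it is about 7 points and at 15% about 11.

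**4. Empty arms.** P(at least one arm with no SAE) = a + b − ab, with a = (1 − p)⁹⁰ and b = (1 − 2p)⁹⁰.
- 2% v 4%: 0.162 + 0.025 − 0.004 = 18%.
- 5% v 10%: about 1%.

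For 8/90 v 0/90 the fitted model gives a coefficient of 22.2 with SE 13810 and Wald p = 0.999. On the same data the likelihood-ratio test gives p = 0.0007, Pearson chi-square p = 0.004 and Fisher p = 0.007.

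**The case against.** **Interval methods belong in the SAP.** Logistic regression yields an odds ratio and interval as standard output, and sparse-data handling is commonly a SAP matter. This stands in part: the absence of an interval method from the protocol would be no finding by itself. But section 11.3 does choose the primary safety model and the significance rule, and that choice suits its objective poorly at the trial's size.

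**A reader might infer that a doubling would usually be missed.** The documents do not support that without a condition. No control SAE rate is given. Participants are hospitalised with moderate to severe disease, and section 8.1 counts death from progression as serious, so 15% or more cannot be excluded; there a doubling would be found 68% of the time or more. HOPE-4's report of no SAEs does not fix the rate here.

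**A reader might infer that p above 0.05 will be taken as showing safety.** No passage says so. The phase II summary in section 2.4 cites a non-significant difference in support of good safety, but for another trial and alongside incidences, intensity and withdrawals. The sentence in section 2.6.3 is background. The listings, laboratory and ECG shifts, events of special interest and the monitoring committee (12.2) also inform any judgement of safety.

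**A reader might infer that the model would hide a real signal.** That needs a Wald test, which the protocol never names. Likelihood-ratio, chi-square and Fisher tests all detect 8 v 0, and the listings would show it.

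Sizing on efficacy is ordinary practice and is not itself an error.

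**Conclusion.** The point holds in a limited form. A primary safety objective is paired with a plain difference test on SAEs, at a size chosen for efficacy. If the control SAE rate is below about 11%, the test misses a doubling more often than not, and a non-significant result then says little about safety. At 15% or 20% the chance of missing it falls to 31-32% or 16%. All of this rests on assumed control rates, because the protocol gives none.

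The weakness of the ordinary odds ratio with an empty arm is real but confined to very low rates, and it affects the estimate and its Wald test rather than every planned analysis. Efficacy conclusions are untouched. This is a cheap improvement.

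**What to change.** In section 11.3, replace the safety sentence by wording to this effect: the primary safety result is the difference between arms in the proportion of participants with at least one SAE in the safety set, with a two-sided 95% Miettinen-Nurminen or Newcombe interval; any odds ratio comes from Firth or exact logistic regression; a p-value above 0.05 is not evidence of safety; and the report gives the SAE excess that cannot be excluded.

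In section 11.1, state that the size was set for efficacy and that, with equal arms at 5-15%, an excess of about 7 to 11 points could not be excluded.

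The cost is wording and one standard interval, with no added participants or data. It does not raise the power to detect harm; it makes the remaining uncertainty visible. The small downside is a visibly weaker safety claim.

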The number of participants was calculated using R 4.0 software, as detailed below: Trial Size: Two Sample Proportion. NIS (alpha = 0.05, beta = 0.2, p1 = 0.667, p2 = 0.281, k = 1, delta = 0.386, margin = 0.205) = 80.043° 81 por Grupo.

Number of participants	Sample Size	Drop-out (10%)
162 being:	180	18
81 Placebo group	90 Placebo group	
81 Azvudine group	90 Azvudine group	

"The required sample size for the IGZ-1 protocol is 180 participants, with 90 participants in each group, considering the 10% chance of drop-outs (participants who leave the study for some reason other than its termination)."

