Univariate analysis of the clinical outcome variables and with the group variable.

- For the secondary efficacy indicator analysis, the coronavirus viral load changes compared to baseline should be calculated for the experimental and control groups separately, as well as the value of the difference between the viral load changes compared to baseline for both groups. The ANCOVA model will be used to estimate the impact of treatment on viral load changes adjusting for other study variables such as disease severity, age, weight, and comorbidities, etc.
 - For analysis of the secondary efficacy indicator one should stratify according to the severity of the disease (severe, severe), following the following statistical methods:

PRIMARY ENDPOINT			ANALYSIS METHOD
•	Propo	rtion of participants with clinical status	Teste t de
	impro	vement [Period: until D15,	Student/Teste de
	appro	ximately 14 days].	Mann-Whitney
	0	The criterion for a participant to have	
		an improvement in clinical status is a	
		decrease on the WHO Clinical	
		Improvement Ordinal Scale in at least	
		one category compared to screening	
		(WHO, Jun/2020).	

SEC	CONDARY OUTCOMES	
•	Proportion of participants with a clinical	Pearson's Chi-
	outcome of cure during the study; [Period:	square test
	until D15, D21, and D28, approximately 14-	
	30 days].	

;	inic	al Trial Design	
		o The clinical endpoint of cure is	Student's t-test /
		defined in this protocol as the	Mann-Whitney
		absence of viral RNA in	test
		collected samples and clinical	
		conditions for	
		hospital discharge.	
	•	Time to normalization of body temperature	Student's t-test /
		(below 37.6c, axillary); [Period: until D15,	Mann-Whitney
		D21 and D28, approximately 14-30 days].	test
		Time to improvement of diarrhea,	Student's t-test /
		myalgia, fatigue, malaise, cough and	Mann-Whitney
		headache; [Period: until D15, D21 and	test
		D28, approximately 14-30 days].	
		Changes in liver and kidney function	Student's t-test /
		baselines, and inflammatory and	Mann-Whitney
		immunological markers: [Period: until	test
		D15, D21 and D28, approximately 14-30	
		days]	
		 Lab tests performed on days D1, 	
		D3, D5, D7, D9, D13, D15, D21,	
		D28, and D60.	
		Evaluation of the time to negative	Student's t-test /
		conversion of SARS-CoV-2 viral load by	Mann-Whitney
		RT-PCR between AZVUDINE (FNC) group	test
		and placebo- control group; [Period: until	
		D15, D21 and D28, approximately 14-30	
		days].	

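### Section 11.3 chooses covariates for the supportive models by univariate significance and does not limit them to variables measured before treatment

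*Protocol*

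**What the plan says.** Under the primary goal, Protocol 11.3 specifies one logistic regression for clinical improvement to D15 and one for serious adverse events, each with a single predictor: "and independent variables allocation group, AZVUDINE (FNC) or PLACEBO". It then adds further models, whose status it gives as "As a support analysis, with exploratory character, both for efficacy and safety". The rule for what goes into these models is that "covariate models will be built as well as other variables that present, in the univariate analysis, statistical significance". The threshold comes from the opening of the same section: "If the p-value is ≤0.05, it is considered that there is statistical significance in the test".

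No candidate list goes with this rule, and nothing limits it to values recorded before randomisation or before the first dose. It also does not say whether a variable is screened against the outcome or against the treatment group.

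Two other statements in 11.3 bear on how the rule might be read. Under the secondary objective the method is "Univariate analysis of the clinical outcome variables and with the group variable". The viral-load ANCOVA is described as "adjusting for other study variables such as disease severity, age, weight, and comorbidities, etc".

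**The concern.** An adjusted model estimates the effect of treatment only if its covariates could not themselves have been changed by treatment. Here a p-value is the only entry condition, so the rule admits variables on the path from drug to outcome.

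PCR clearance shows the risk:

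- It is measured repeatedly after randomisation (every two days, section 7).
- The protocol expects the drug to speed it up (2.6.2 and 2.6.3).
- Two consecutive negative tests end treatment and are one of the criteria for discharge (synopsis).
- It is part of the outcome scale: score 0 in Table 4 requires that no viral RNA is detected.

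A variable this close to the outcome will usually pass a univariate screen. A real benefit could then be reported as not confirmed after adjustment. The same logic applies to a laboratory change lying between drug and SAE. In addition, selection by significance suits an SAE model poorly if events are few.

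**Working it through.** **The plan's own figure.** Section 11.1 gives "alpha = 0.05, beta = 0.2, p1 = 0.667, p2 = 0.281, k = 1, delta = 0.386, margin = 0.205" and 80.043, rounded up to 81 per group. With the unpooled superiority-by-margin formula:

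n = [0.667×0.333 + 0.281×0.719] × (1.645 + 0.842)² / (0.386 − 0.205)² = 80.04, so 81.

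Then 81/0.9 = 90 per group and 180 in total. The figure reproduces, though only with a one-sided 5% level. That is a separate matter and nothing below depends on it.

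**Unadjusted effect at the protocol's rates.** (0.667/0.333) / (0.281/0.719) = 5.13.

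**Set-up.** Clearance M is a yes/no variable with probability c1 on azvudine and c0 on placebo. The protocol gives no such rates, so they are assumed and varied. Improvement rates are fixed at 66.7% and 28.1%, with 90 per arm. Three logistic models are fitted in each simulated trial: improvement on treatment, on M, and on both. Adjusted results are for the model containing M, over all fitted trials.

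**Full mediation** (treatment acts only through M). Let q1 and q0 be the improvement rates with and without clearance. Then q1 − q0 = 0.386/(c1 − c0) and q0 = 0.667 − c1(q1 − q0).

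- 90% vs 35%: q1 − q0 = 0.386/0.55 = 0.702, q0 = 0.035, q1 = 0.737. Feasible.
- 85% vs 35%: q1 − q0 = 0.386/0.50 = 0.772, q0 = 0.011, q1 = 0.783. Feasible.
- 80% vs 40%: q1 − q0 = 0.386/0.40 = 0.965, q0 = 0.667 − 0.772 = −0.105. Impossible.

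At the protocol's rates, full mediation therefore needs a very large clearance gap.

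**Partial mediation.** For a clearance–outcome log odds ratio b, solve c0·expit(a+b) + (1−c0)·expit(a) = 0.281 for a, and c1·expit(t+b) + (1−c1)·expit(t) = 0.667 for t. The direct log odds ratio is t − a.

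| Clearance | Clearance–outcome OR | M passes outcome screen | Median adjusted OR | Adjusted result significant |
|---|---|---|---|---|
| 90% vs 35% | full mediation | 92% | 0.97 | 2.9% |
| 85% vs 35% | full mediation | 62% | 0.98 | 3.3% |
| 80% vs 40% | 3 | 99.8% | 3.60 | 97% |
| 80% vs 40% | 10 | 100% | 2.78 | 81% |
| 80% vs 40% | 30 | 99.6% | 2.48 | 59% |
| 70% vs 50% | 3 | 98.4% | 4.51 | 99.8% |
| 70% vs 50% | 10 | 100% | 5.06 | 99.0% |
| 70% vs 50% | 30 | 100% | 6.39 | 100% |

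The unadjusted model was significant in essentially every trial, with median OR 5.0 to 5.2. The full-mediation rows use 1,000 runs (986 and 915 could be fitted), the others 500. The upward shift in the last row occurs because an odds ratio conditional on a strong predictor differs from the marginal one, which here outweighs the part of the effect removed.

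**The screen ignores treatment.** With clearance 80% vs 40% and no effect of clearance on improvement, clearance still passes the outcome screen in 56% of trials. Its entry is harmless in that case (median adjusted OR 5.41 against 5.20 unadjusted).

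**A smaller effect.** Assume 81 per arm, clearance 65% vs 40%, and improvement depending only on clearance, giving 68.0% vs 58.2%. The true OR is (0.680/0.320)/(0.582/0.418) = 1.53. Repeated simulations gave a median OR of 1.52 to 1.54 before adjustment and 0.99 to 1.01 after it. Significant results fell from 24–26% to 5–6%. Clearance was selected in over 99% of runs when screened against the outcome, and in about 89–90% when screened against group.

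**SAE model.** The protocol gives no expected SAE rate. At assumed rates of 2%, 5% and 10%, 180 participants yield about 4, 9 and 18 events (180×0.02 = 3.6; 180×0.05 = 9; 180×0.10 = 18).

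**The case against.** The sentence is garbled, and baseline covariates may have been meant. A reader might infer from the secondary-objective line that the screen is aimed at post-randomisation variables. The document does not support that. The line stands under a different heading and nothing ties it to the covariate rule. Section 11.3 also describes univariate comparison of the two groups under general conditions, which naturally covers baseline characteristics. The only adjustment variables it names, those of the viral-load ANCOVA, are of baseline type, with only the closing etc. left open. The relation between viral load and clinical outcome has its own secondary analysis. All of this stands, so the point is what the rule permits, not what it directs.

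It can also be said that candidate lists for exploratory models belong in the SAP. That is true of a list. But 11.3 fixes a selection rule, and an SAP that followed it would inherit the gap.

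Finally, these models are exploratory, and no primary test or error rate depends on them. This also stands and limits the severity. It does not make the point empty, because they are presented as support for the primary efficacy and safety results.

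**Conclusion.** The point holds in a limited form. The stated rule allows a variable affected by treatment into the supportive models. If one enters, the adjusted odds ratio is no longer an estimate of the treatment effect.

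Size and direction depend on clearance rates and on a clearance–outcome association that the protocol does not give. Over the assumptions shown, the result runs from erasure through attenuation to little change or a modest rise. It would be wrong to infer that adjustment generally erases the effect. At the protocol's rates that needed full mediation, found feasible here with clearance gaps of 50 to 55 points. The possibility that an SAE excess would be adjusted away is reasoning by analogy and was not calculated.

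The unadjusted primary models and the sample size of 180 are unaffected. Severity is minor to moderate: a worthwhile improvement, not a threat to the main conclusion.

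**What to change.** Replace the selection rule in 11.3 with wording such as:

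> Supportive models adjust for a short list of covariates named before unblinding and measured before the first dose (for example baseline WHO score or disease severity, age, comorbidities). No variable measured after randomisation enters, and none is selected by significance. The SAE model is limited to at most one baseline covariate if events are few.

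The list itself can sit in the SAP, since section 5.4.4 already requires the final statistical plan before unblinding. Any model containing post-randomisation variables should be labelled separately as a mediation or exploratory analysis.

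The cost is a few sentences. No new data are needed: the screening WHO score is required by the primary endpoint, and age and medical history are collected at visit 1. The downside is that a prognostic variable found later cannot be added to this model.
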